### **Study Design & Methods**

Potential participants will be screened by study staff using a brief self-report format phone screening to make sure that they meet eligibility criteria before scheduling the first assessment where they will complete the informed consent process. Study staff will obtain verbal consent prior to asking the caller any screening questions.

If requested and preferred by potential participants, we will send them a link to complete the screening questions through webdataxpress. This link to the WDX screening form will also be available on our lab website. Individuals will have to consent to the screening process on the site before moving on to the screening questions. After answering the screening questions potential participants will be presented with different responses depending on eligibility status. If ineligible: Thank you for your interest in the HABIT Study. Based on the answers you provided in this screener, you are ineligible to participate in our study. We will keep you in mind for any future studies. Have a great day!

If eligible: Thank you for your interest in the HABIT Study. Based on the answers you provided in this screener, you are eligible to participate! A member of our team will reach out to you within a week or so to schedule an assessment and answer any further questions you may have. Have a great day!

If we need more information to determine eligibility: Thank you for your interest in the HABIT Study. A member of our team will reach out to you within a week to discuss your potential participation and answer any further questions you may have. Have a great day!"

Assessments: All participants will complete assessments at 16 weeks of pregnancy or less (T0), Between 32 and 40 weeks (T1), at 6 months postpartum (T6) and 12 months postpartum (T12). Assessments will be conducted by research assessors. Assessments will take place at Magee-Womens Hospital and each assessment should take 1-2 hours to complete. Assessments will consist of the following: (Questionnaires and a schedule of assessments are attached and described below)

Height, weight & waist circumference. Height will be measured with a stadiometer at study enrollment (T0). Weight will be measured using a calibrated digital scale at all assessment timepoints. Women will be measured in street clothes without shoes. Prepregnancy body mass index (BMI) will be calculated as (weight in kg)/(height in m2). The use of self-reported pregravid weight is common in studies of gestational weight gain and accurate within 1-2 kg. Repeated measurements of weight will also be abstracted from medical charts during pregnancy. Waist circumference will be measured at T0, T6 and T12. This will be taken using a tape measure marked in centimeters and placed at the level of the umbilicus. The average of two consecutive measurements will be used.

Gestational weight gain and excessive gestational weight gain. Gestational weight gain (GWG) will be calculated as final weight before delivery minus prepregnancy weight. GWG will be defined as excessive according to IOM guidelines based on initial prepregnancy BMI. Both the categorical (yes/no) variable representing GWG above the IOM guideline for the woman's prepregnancy BMI, and the total amount of GWG will be used as dependent variables. Because the length of gestation is a potential confounder of GWG, we will abstract delivery date from women's medical charts and calculate gestational length.

Demographic information. Information including age, race, ethnicity, income, educational background, employment status, health insurance status and marital status will be collected at T0 and updated at T1, T6 and T12.

Self-reported mood. Women will complete the Center for Epidemiological Studies-Depression Scale (CES-D) to assess current depressive symptomatology. The CES-D was selected because it appears to be less sensitive than other depression scales to somatic symptoms that may be common postpartum. Thus, the CES-D provides a useful repeated measure during pregnancy and the postpartum period. Responses on the CES-D will be carefully reviewed, and women who endorse extreme scores will be contacted for further evaluation and referral if necessary. This questionnaire will be completed at all 4 assessments. The Edinburgh Postnatal Depression Scale (EPDS) will be given at all 4 timepoints. This measure of depression specifically looks at postnatal depression. Participants will read 10 statements and for each one choose which of four possible responses is closest to how she has been feeling during the past week. Anxiety will be measured by the State Trait Anxiety Inventory (STAI). 20 questions are rated on a 4 point scale with higher scores indicating higher anxiety. This questionnaire will be completed at all timepoints.

Sleep quality. The Pittsburgh Sleep Quality Index will be given at all timepoints to assess sleep quality.

Sleep chronotype. A modified version of the Munich ChronoType Questionnaire (MCTQ) will be used at all timepoints to assess sleep chronotype. This self report questionnaire has questions designed to collect more detailed information on sleep patterns.

Sleep health. The RU\_SATED 4.0 Sleep Health Scale will assess participants' multidimensional sleep health at all timepoints (Baseline, T0, T1, T6, and T12). It is a 6-item measure that assesses sleep over the past month.

Infant sleep. The Brief Infant Sleep Questionnaire - Revised (BISQ) Short Form will be used to assess infant sleep patterns at T6 and T12. The BISQ is a parent-completed measure of infant and toddler sleep. The BISQ assesses start of the bedtime routine, bedtime, sleep onset latency, night waking frequency, night waking duration, longest stretch a child remains asleep, total nighttime sleep, nap duration, and total amount of time a child sleeps in a 24-hour period. Higher scores on the BISQ indicate better sleep.

Stress. Perceived stress will be assessed using the Perceived Stress Scale(PSS). The PSS is a 14item scale designed to assess the degree to which an individual appraises situations as stressful. This questionnaire will be given at all assessments.

Impulsivity. The UPPS-P Impulsive Behavior Scale will be used as a general measure of impulsivity. The UPPS-P is a 59-item measure that assesses five facets related to trait impulsivity. The items comprising the measure consist of Likert scale response options. Participants will complete select subscales that have a total of 33 questions. The Barratt Impulsiveness Scale will be used to assess the personality/behavioral construct of impulsiveness. This questionnaire has 30 questions rated on a 4 point scale. Both of these questionnaires will be complete at T0, T1 and T6. Another measure of impulsivity that participants will complete at each timepoint is the Consideration of Future Consequences Scale. This is a self-report questionnaire that comprises 14-items measuring a tendency to consider future consequences of behavior.

Eating. The Eating Disorder Examination Questionnaire (EDE-Q) is a self-report version of the Eating Disorder Examination. The EDE is an interview designed to assess the complete range of psychopathology and behaviors related to disordered eating. Participants will complete the Three Factor Eating Questionnaire, which contains three empirically derived factors with good internal consistency in nonclinical samples. The restraint factor reflects conscious thoughts and purposeful behaviors to control food intake. Disinhibition reflects a tendency to relinquish control over food intake in response to environmental or emotional stimuli. The final factor is hunger. Both of these questionnaires will be completed at all timepoints. In addition, participants will also complete 2 dietary food recalls at each assessment. The study will utilize the Automated Self-Administered 24-hour (ASA24) Dietary Recall System to collect information about what participants ate in the prior 24 hours. At each timepoint participants will complete 2 separate 24 hour food recalls. The first at their in person assessment and another other one over the phone within the next couple weeks. At the end of the 12-month follow-up recalls interviewers will ask participants LOC questions (attached in question 2). The Perceptions about Eating and Weight during Pregnancy will be administered during T0 and T1 assessments. This questionnaire will measure eating and weight concerns and potential misconceptions about eating and weight specific to pregnancy. The Power of Food Scale (PFS) will be complete at each assessment timepoint. This is used to assess appetite for palatable foods and document the psychological impact of living in environments with an abundance of palatable foods. The Eating Pathology Symptoms Inventory (EPSI) will assess body image dissatisfaction and eating pathology symptoms in this study at T12 only.

Weight Bias- The Weight Bias Internalization Scale (WBIS-M) will be used at all timepoints. This measure contains 11 questions on weight bias that are rated on a 7-point Likert scale.

Physical activity- The Pregnancy Physical Activity Questionnaire (PPAQ) will be used to assess activity during each assessment. The PPAQ is a self-report measure of physical activity which evaluates the duration, frequency, and intensity of physical activity amongst pregnancy women. As an additional, objective, measure of activity, participants will be asked to wean an activity tracker for a period of time at each assessment timepoint.

Appetite and feeding. The Adult Eating Behaviour Questionnaire (AEBQ) will be used to measure the appetitive traits of our participants. The AEBQ is a self report questionnaire with 35 item rated on a 5 point scale. Participants will complete this questionnaire at each assessment. The Baby Eating Behaviour Questionnaire (BEBQ) will be used to measure the appetites of our participants' infants. Mothers will report their child's appetite by answering 18 questions rated on a 4 point scale. This questionnaire will be completed at the T6 assessment. A questionnaire about the participant's intent to breastfeed will be administered at their T1 assessment and at T6 and/or T12 they will complete a questionnaire (CEBQ) will be completed during the T12 assessment to measure the appetites of our participants' child. Participants will complete this 35 item scale reporting on their 1 year old child.

Health information. We will collect, via questionnaire, interview format and medical record review, information about use of medications, including psychiatric medications, use of other treatments for weight, and the presence of medical conditions (e.g., gestational diabetes) at each assessment. We also will collect information about parity and current family composition (i.e., number of children and adults living in the home) as well as current and past pregnancy data via questionnaire. Information about current smoking status and history of smoking will be collected using a self-report questionnaire. The same questionnaire will also ask about past and current alcohol use. An investigator designed Cannabis Use Questionnaire will be used to evaluate current and past cannabis use. This measure will be used at all timepoints. Medical record review. Research assessors will look at participants' medical charts to extract physician measured weights, verify that they are having a singleton pregnancy, delivery date, and medical history during the pregnancy (e.g. current and preexisiting medical conditions, medications, and other treatments being pursued). We will also use participant's medical records to facilitate counseling sessions by looking up or verifying their next obstetric appointment date and time.

Mindfulness. To assess mindfulness, the Mindfulness Attention Awareness Scale (MAAS) will be used. This scale contains 15 items rated on a 6 point scale and it has been shown to be valid and reliable. Participants will completed this measure at each of the 4 timepoints. Body Surveillance. Participants will complete a subscale of the Objectified Body Consciousness Scale (OBCS) to measure body surveillance, which closely matches self-objectification, or the "habitual monitoring of the body's outward appearance". This subscale contains 8 questions on a 7 point Likert scale. Participants will complete this measure at each of the 4 timepoints.

Food insecurity- Food insecurity will be measured using an investigator edited version of the U.S. Household Food Security Survey Module. This questionnaire will be given at all assessment visits.

Discrimination. The Major Experiences and Everyday Discrimination Scales include 19 interviewer administered questions. The Major Experiences subscale includes 9 questions about employment, housing,

and education; the Everyday Discrimination subscale includes 10 questions about interactions with others (e.g., respect, harassment). Reasons for discrimination (e.g., race, gender, religion) are assessed. This interview will be administered at all timepoints.

Adverse childhood experiences will be measured using the BRFSS Adverse Childhood Experience (ACE). The measure was edited to also include some questions of emotional and physical neglect. This questionnaire will be given at T12.

Measure of behavior change- An investigator designed measure of behavior change will be used at all timepoints. This measure contains 44 questions which were designed to evaluate topics addressed throughout HABIT treatment such as exercise, eating, sleep and social support.

Program evaluation- The program evaluation form is an investigator designed questionnaire to allow HABITpreg and HABITpost participants to give feedback on the study intervention. They are able to rate how helpful the program was, how much they enjoyed the program, and provide written feedback/suggestions. The form includes questions about their experience with the virtual format of the intervention during COVID-19. The measure will be given to pregnancy intervention participants at the T1 assessment and postpartum intervention participants at the T6

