### Intervention:

By study design participants will be randomized twice over the course of their participation. Once at enrollment and again at the time of their second assessment which coincides with the end of their pregnancy. After completing the baseline assessment (T0), participants will be randomized to either the HABIT intervention during pregnancy or to usual care. Usual care consists of the care that pregnant woman usually receive from their obstetric and other providers. All women in the study will continue to receive the care they usually receive. Those in usual care will not receive any extra treatment from the study team. If they are randomized to treatment they will be assigned a coach and will immediately get started with their first session. Treatment during pregnancy will consist of up to 10 in person sessions lasting approximately 20-30 minutes. These sessions will take place at their regularly scheduled OB appointments, at our research building, or a nearby location. Participants in the HABIT pregnancy group will also receive texts and phone calls between sessions. HABIT will focus on weight, physical activity, eating and psychosocial issues. Intervention goals will emphasize adherence to healthy behaviors rather than absolute weight goals. Specifically, women will receive consultation about nutritional balance, dietary guidelines for pregnant women and advice to maintain an optimal rate of weight gain according to prepregnancy BMI. Women will use self-monitoring forms to identify and modify cues for unhealthy behaviors. Beliefs about body weight and eating during pregnancy

will be addressed and effects of physical activity on body weight, health, and mood will be included. Mood will be monitored by the EPDS questionnaire to help tailor individualized treatments. To help facilitate treatment, participants who need them will be provided with smart phones and Bluetooth enabled scales. Participants who are assigned to usual care will not have regular contact with study staff.

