### **Eligibility Criteria**

Women will be eligible if they: (1) have a prenatal BMI  $\geq 25$ ; (2) are at or before 17 weeks and 4 days of gestation; (3) are English speaking and (4) have a singleton pregnancy. We considered an upper limit to BMI. However, given the paucity of data on weight outcomes for women with BMIs >35, we elected not to limit BMI but will randomize women in two strata according to BMI (25-29.9 vs.  $\geq$ 30). Similarly, parity may impact perinatal weight, but intervention goals are similar for primagravidae and multiparous women. Thus, we will recruit women regardless of gravida and parity, and include these variables as covariates in all analyses.

With the approval of modification #20: (5) Identify as Black or Multiracial Black

Infants will be eligible for medical record and microbiome data collection if (1) mothers' are

enrolled into HABIT after MOD16020497-12 or (2) if we are able to reconsent their mothers' during the T1 or T2 timepoints.

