There are 8 sequences or combinations of intervention in this SMART, which we use to define group for hypothesis testing. Time also is a generic factor, and the number of levels will depend on the outcome being modeled. For example, for weight, mood and stress, time will be a linear term beginning at baseline, and a quadratic term will be added to the model if necessary. For other outcomes, time will be a factor with 4 levels (baseline, end of pregnancy, and 6- and 12-months postpartum). We also will evaluate the need to control for the effects of potential confounds such as race, age, socioeconomic status (fixed covariates) as well as breastfeeding, smoking status and physical activity (time-varying covariates). If the coefficients for groups or group by time interactions are significant, planned contrasts will evaluate groups on weight and related outcomes at 6- and 12-months postpartum. Additionally, we will create a binary variable for 5% weight loss and use generalized mixed-effect models with the logit link to compare groups on proportions with 5% loss at 6- and 12-months postpartum.

Finally, to fully utilize a SMART design, and to evaluate the utility of using GWG as a tailoring variable, we will explore what the optimal strategy is and for which participants. A dynamic strategy is a decision rule about which intervention is best initially and what intervention follows, depending on the response status. The proposed deisgn produces HABITpreg and TAU during pregnancy, and women who do and do not meet IOM guidelines for GWG each have HABITpost and TAU postpartum, resulting in the 8 possibilities sequences.

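### Comparisons of HABITpreg with usual care on gestational weight gain include gain before randomisation and recall error; adjusting for baseline values already collected would sharpen them at almost no cost

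*Combined protocol and SAP*

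**What the plan says.** The GWG paragraph of Study Design & Methods gives the definition: "Gestational weight gain (GWG) will be calculated as final weight before delivery minus prepregnancy weight". It names two outcomes built on it, the yes/no variable for gain above the IOM guideline "and the total amount of GWG will be used as dependent variables". The only source mentioned for prepregnancy weight is in the paragraph before: "The use of self-reported pregravid weight is common in studies of gestational weight gain and accurate within 1-2 kg". The GWG sentence itself does not name its source, so self-report is an inference, though a strong one. The same section provides a measured starting point: "Weight will be measured using a calibrated digital scale at all assessment timepoints", which includes T0.

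On timing, the Intervention section says: "After completing the baseline assessment (T0), participants will be randomized to either the HABIT intervention during pregnancy or to usual care". How late T0 can fall is stated in two ways. The assessment schedule reads "All participants will complete assessments at 16 weeks of pregnancy or less (T0", while under Eligibility Criteria women may enter if they "are at or before 17 weeks and 4 days of gestation".

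On analysis, Statistical Considerations puts the BMI stratum in every mixed model and will consider race, age and socioeconomic status. Eligibility Criteria promises gravidity and parity as covariates in all analyses. Gestational length is to be derived because it may confound GWG. No section adjusts GWG for T0 weight, for gain before T0 or for gestational age at T0.

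GWG has a second role. Statistical Considerations says "A dynamic strategy is a decision rule about which intervention is best initially and what intervention follows, depending on the response status", and meeting or exceeding the IOM guideline is the status that, with the two assignments, yields the eight sequences.

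**The concern.** Total GWG is the sum of three parts: true gain from conception to T0, the error in reported prepregnancy weight, and gain from T0 to delivery. A prenatal intervention that starts after T0 can act only on the third. In a comparison of prenatal arms the first two are noise, and most of that noise is observable at baseline, because T0 weight minus reported prepregnancy weight contains both.

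At stake is the precision of the prenatal comparison on GWG. The Scientific Background says earlier interventions did not help overweight and obese women avoid excessive gain, so a noisier outcome makes another inconclusive result more likely. The 1-2 kg accuracy figure is also not small next to the IOM upper limits, so some women near the limit will be classified partly on recall.

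**Working it through.** The documents supplied give no SD, effect size, sample size or power for GWG, so there is no design figure to reproduce. The check has three parts.

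**1. How much of pregnancy precedes treatment** (40-week pregnancy assumed)
- Eligibility limit: 17 + 4/7 = 17.57 weeks; 17.57/40 = 44%.
- Assessment schedule: 16/40 = 40%.

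These are upper bounds on a share of time, not of weight gained.

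**2. The stated 1-2 kg against the IOM upper limits** (limits from the Scientific Background; 1 lb = 0.4536 kg)
- Overweight: 25 lb = 11.3 kg, so 1-2 kg is 9%-18% of the limit.
- Obese: 20 lb = 9.1 kg, so 1-2 kg is 11%-22% of the limit.

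**3. What adjustment would save on total GWG**

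Let A be the SD of true gain before T0, E the SD of self-report error, B the SD of gain from T0 to delivery, and r the correlation between the two gains, with c = r × A × B. Self-report error is taken as independent of both gains, and error in the T0 weight is ignored.
- Unadjusted variance: A² + E² + B² + 2c.
- Residual variance after adjusting for apparent pre-T0 gain: B² − c²/(A² + E²).

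All four inputs are assumptions: A 2-4 kg, E 1-2 kg, B 4-6 kg, r 0-0.3.

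| Case | A, E, B, r | Unadjusted | Adjusted | Reduction | Ratio |
|---|---|---|---|---|---|
| Smallest | 2, 1, 6, 0 | 4 + 1 + 36 = 41 | 36 | 12% | 1.14 |
| Middle | 3, 2, 5, 0 | 9 + 4 + 25 = 38 | 25 | 34% | 1.52 |
| Largest | 4, 2, 4, 0.3 | 16 + 4 + 16 + 9.6 = 45.6 | 16 − 4.8²/20 = 14.8 | 67% | 3.1 |

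The ratio of variances is the factor by which an unadjusted analysis would need more women for the same precision, so the middle case corresponds to about 1.5 times the sample.

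**Equivalence in the linear model.** Total GWG equals T0-to-delivery gain plus apparent pre-T0 gain. With apparent pre-T0 gain as a covariate, moving it to or from the outcome changes only its own coefficient, by exactly 1. The treatment coefficient and its standard error are the same whether the outcome is total GWG or gain from measured T0 weight. This does not carry over to the logistic model.

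**The case against.** The case on the other side is substantial.

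- **No hypothesis tests GWG as an outcome.** Every aim for the women in Study Objectives concerns weight, cardiometabolic health, depressive symptoms and stress at 12 months postpartum; in Hypotheses 3 and 4 GWG only classifies women. The weight model already runs from baseline. This stands and limits the importance of the point. GWG is nevertheless a named dependent variable with no stated handling of its pre-randomisation part.
- **The definition is deliberate.** IOM limits are set by prepregnancy BMI and apply to total gain, so the yes/no variable needs total gain. This stands. The definition is not an error, and nothing here argues for changing the tailoring rule.
- **Other covariates are planned.** They include gravidity and parity and possibly race, age and socioeconomic status. This stands, and it means a comparison with a wholly unadjusted analysis somewhat overstates the saving. None of these variables measures gain before T0, and gestational length is known only at delivery.
- **The size is assumed.** This stands. The accuracy statement is read here as an error SD; read as a bound it implies a smaller SD, and read as a constant bias it adds no variance. The 67% end needs earlier gain to vary as much as later gain. The variance figures do not apply to the yes/no outcome.

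A reader might infer two stronger things. The first is that the effect of HABITpreg on GWG is biased or diluted. It is not: randomisation follows T0, so earlier gain and recall error are balanced in expectation and the difference in kilograms is intact. Only the standard error grows, and with it the effect of chance imbalance. The second is that women who gained much before T0 will be scored as exceeding the guideline whatever HABITpreg does. That needs gain already at or near the upper limit. If pre-T0 gain were normal with mean 1-4 kg and SD 2-4 kg (assumed), at most about 10% of obese and 3% of overweight women would be over the limit by T0. Such women are more likely to be scored as exceeding, not certain to be.

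**Conclusion.** The point holds as a free improvement in precision for the prenatal comparison on GWG. It is not a flaw in the trial's main comparison at 12 months. As planned, both GWG outcomes carry gain before randomisation and recall error, and no listed covariate removes them. For total GWG the avoidable residual variance is about 12% to 67%, with 34% in a middle case, against an unadjusted analysis and entirely under assumed SDs. The direction is the same across the whole assumed range. For excessive GWG the same mechanism applies, but no size is claimed. The upper bound on the pre-treatment period is 16 weeks or 17 weeks 4 days, depending on which section is read; the two must be reconciled, but the conclusion is the same under either.

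**What to change.** In analyses comparing prenatal arms on GWG, prespecify two further baseline covariates alongside the BMI stratum, gravidity and parity: pre-T0 gain (T0 weight minus reported prepregnancy weight) and gestational age at T0.

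- **Total GWG:** a linear model with these covariates.
- **Excessive GWG:** a logistic model with the same covariates. State that its odds ratio is conditional on them, or report a standardised risk difference.
- **Tailoring:** keep total GWG against the IOM range as the classification for the sequences.
- **Clarify:** state the source of prepregnancy weight, and reconcile the T0 window with the gestational limit for entry.
- **Remote baselines:** the COVID-19 text at the end of the Intervention section allows baseline weights on scales dropped off at home or elsewhere. Flag these T0 weights and say how a missing one is handled.

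The cost is a few sentences in the analysis plan. T0 weight is already scheduled, prepregnancy weight is needed for BMI, and gestational age is needed for eligibility. All three describe the woman before randomisation, so adjusting for them introduces no post-randomisation bias. The one thing to manage is how the adjusted odds ratio is interpreted.

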After participants complete the T1 assessment towards the end of their pregnancy they will again be randomized to either receive HABIT treatment postpartum or to receive usual care. All participants will be randomized again. Usual care consists of the care they would usually receive from their OB and other providers. All women will continue to receive this care, however, those assigned to usual care will not receive any additional treatment from the study. If participants are assigned to HABITpostpartum they complete a separate intervention of over the 24 weeks immediately following delivery. Treatment will consist of 12 biweekly sessions completed over the phone or in person. In person sessions will be done at the participant's home or another convenient location. Additionally, participants will receive calls and texts between sessions. Mood will be monitored by the EPDS questionnaire to help tailor individualized treatments. All participants will continue to receive their standard postpartum care from their medical team. Counseling sessions during pregnancy and postpartum will be conducted by research project staff that has, at least, masters level or equivalent degrees. Counselors will be trained by [name] prior to the start of the project. To help facilitate treatment, participants who need them will be provided with smart phones and Bluetooth enabled scales. Treatment materials are attached to the end of this application.

Treatment sessions will be audio taped for supervision.

All newly enrolled participants and any previously enrolled participant that has not yet delivered her baby will be invited to participate in the ancillary study. Women who agree to participate in the ancillary study will complete additional assessments at each HABIT timepoint and an additional assessment between delivery and 4 weeks postpartum. During these assessments they will complete the following:

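### Nothing requires the second T0 dietary recall or the T0 tracker wear to be finished before randomisation, so these baselines may be collected after HABITpreg has begun

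*Combined protocol and SAP*

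**What the plan says.** The relevant statements are spread over three sections of the combined protocol and SAP.

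- **Diet (Study Design & Methods, Eating).** "participants will also complete 2 dietary food recalls at each assessment". Their timing is: "The first at their in person assessment and another other one over the phone within the next couple weeks".
- **Activity (Study Design & Methods, Physical activity).** The PPAQ questionnaire is completed during each assessment. For the objective measure, "participants will be asked to wean an activity tracker for a period of time at each assessment timepoint". The length of wear, the way trackers are issued and the position of the wear relative to randomisation are not given.
- **Visit length (Study Design & Methods, Assessments).** An assessment is expected to last one to two hours.
- **First randomisation (Intervention).** The two randomisations are placed as follows: "Once at enrollment and again at the time of their second assessment which coincides with the end of their pregnancy". The operative sentence is: "After completing the baseline assessment (T0), participants will be randomized to either the HABIT intervention during pregnancy or to usual care".
- **Start and content of HABITpreg (Intervention).** "If they are randomized to treatment they will be assigned a coach and will immediately get started with their first session". On content: "HABIT will focus on weight, physical activity, eating and psychosocial issues".
- **HABITpost (Intervention).** Women assigned to it after T1 are told that "they complete a separate intervention of over the 24 weeks immediately following delivery".
- **Analysis (Statistical Considerations).** Baseline measures are compared between HABITpreg and TAUpreg. For outcomes other than weight, mood and stress, time is a four-level factor that includes baseline. Physical activity is listed as a possible time-varying covariate.

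**The concern.** A baseline value should be fixed before allocation, or at least before treatment can act on it. Here one of the two T0 recalls follows the visit by up to about two weeks, and a wear period cannot be completed within a one- to two-hour visit. If allocation is released at the end of the visit, the second recall falls after it. In HABITpreg, but not in usual care, it would also usually fall after a session aimed at the behaviour being measured.

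That asymmetry is what matters. In the planned baseline comparison, a genuine early response would look like a chance imbalance or a randomisation failure. In an analysis of diet or tracker activity that measures change from T0, tests group by time with T0 as one level, or adjusts for T0, part of the HABITpreg effect would be subtracted from itself. If tracker data supply the physical-activity covariate, its T0 value could likewise already reflect treatment.

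**Working it through.** The plan gives no figure on this point, so there is none to reproduce. The check is on the order of procedures, followed by a conditional illustration of size.

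**Step 1. Two readings of the order.**

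| | Reading A | Reading B |
|---|---|---|
| What completing T0 means | Both recalls (and wear) done | The single visit done |
| Second recall | Before allocation | After allocation |
| Tracker wear | Before allocation | After allocation, if wear follows the visit |
| In-person recall, PPAQ | Before allocation | Before allocation |

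Reading A rests on counting both recalls as part of the assessment and randomising only once that assessment is complete. Reading B rests on the visit length, on randomisation being placed at enrolment, and on the immediate first session.

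T1 helps to choose between them. The second randomisation is also described as following completion of T1, yet it is placed at the time of that assessment. T1 may be as late as 40 weeks. Taking a couple of weeks as about 2, waiting for the second recall could delay allocation to 40 + 2 = 42 weeks, although HABITpost is meant to start at delivery. Completion therefore more naturally means the visit. Reading B is the likelier, but Reading A is not excluded.

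**Step 2. Size under Reading B (illustration).** Let δ be the later HABITpreg effect on a diet measure and f the share of it present at the second recall. Both f and the averaging of the two recalls are assumptions; the plan states neither.

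- Baseline = (R1 + R2)/2. In HABITpreg, R2 carries fδ, so the baseline carries fδ/2.
- Change-from-baseline contrast = δ − fδ/2 = δ(1 − f/2).
- With adjustment for baseline at slope b (assumed 0.3 to 0.7), the contrast is δ(1 − bf/2).

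| f (assumed) | Change contrast keeps | Loss | Adjusted contrast keeps (b = 0.3 to 0.7) |
|---|---|---|---|
| 0 | 100% | 0% | 100% |
| 0.25 | 87.5% | 12.5% | 96.3% to 91.2% |
| 0.5 | 75% | 25% | 92.5% to 82.5% |
| 1 | 50% | 50% | 85% to 65% |

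For scale, take a change contrast with 80% power at f = 0 and two-sided 5% significance. With an unchanged standard error, its power becomes Φ[(1.960 + 0.842)(1 − f/2) − 1.960], which is about 69%, 56% and 29% for f = 0.25, 0.5 and 1.

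No corresponding figure is offered for the tracker, because its timing is not stated.

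**Step 3. Which analyses are exposed.** These are the baseline comparison and any diet or tracker analysis that uses T0 as a reference, a time level or a covariate. In the four-level model, contrasts at 6 and 12 months with free group-by-time means do not use the T0 value directly. They are, however, reached only if a group or group-by-time coefficient is significant, and T0 contributes to the group-by-time term.

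**Step 4. T1.** HABITpost starts at delivery, not at the second randomisation. A T1 recall or wear period is exposed only if delivery comes before it, which is possible for late T1 visits. The documents give no figure for how often.

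**The case against.** The best defence is Reading A: both recalls belong to the assessment, and randomisation follows its completion. On that wording the order is already correct. The word immediately runs from randomisation, not from the visit, and the mention of enrolment can be read as a summary. Sessions may be held at routine obstetric appointments, and staff may look up the next appointment to arrange counselling, so a gap between the T0 visit and the first session is compatible with the text. The protocol also refers to an attached schedule of assessments, not in the text supplied, which may settle the order. This stands as far as it goes: the order is not stated either way, and one sentence would resolve it.

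Second, the consequences are limited. Diet and activity are not named outcomes of Aim 1 or Aim 2, no diet change contrast is specified, and no rule says that the recalls are averaged. This also stands, and it keeps the point away from the main result. An f of 1 would mean that the whole effect of up to ten sessions is present within about two weeks, so the 50% loss is an extreme.

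A reader might infer three stronger things that the documents do not support:

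- That these baselines are in fact post-randomisation and already contain treatment effect. The order is probable for the recall, only possible for the tracker, and documented for neither; no early effect is documented either.
- That all baseline diet and activity data are affected. The in-person recall and the PPAQ precede allocation on either reading.
- That the same fault recurs at T1. It does not, because the postpartum programme begins at delivery.

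**Conclusion.** The point holds in conditional form. The supplied text has no rule that keeps the second T0 recall and the T0 tracker wear ahead of allocation and the first HABITpreg session, and for the recall the wording points more toward the wrong order than the right one. Confidence is high that the rule is missing from that text and moderate about the order followed in practice.

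If the order is as feared, and the early effect has the same direction as the later one, baseline-anchored diet or tracker analyses are biased toward no HABITpreg effect and the baseline comparison can mislead. The 12.5% to 50% loss for a change contrast depends on Reading B, on averaging the two recalls and on an assumed f of 0.25 to 1; it is not an estimate for this trial. The weight result is not directly affected. The point is worth correcting because the remedy is cheap and works under either reading.

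**What to change.** - **Define baseline by date.** In Statistical Considerations, state that baseline diet and activity are data dated before randomisation: the in-person recall, the PPAQ, and any second recall or tracker wear that did precede allocation. Record the dates of recalls, wear, randomisation and first session.
- **Reclassify the rest.** Treat T0 recalls or wear dated after randomisation as post-randomisation data. Keep them out of the baseline comparison and do not use them as baseline values or for baseline adjustment. This also covers women already enrolled.
- **Prospective alternative.** State the wear period, and release allocation only once the second recall and the wear are complete. Both must follow consent, which Study Design & Methods places at the first assessment, so moving them ahead of the T0 visit is not an option under the current procedures.
- **T1.** Classify any T1 recall or wear dated after delivery as postpartum.

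The cost is SAP wording and use of dates, with no new measurements. Where only the in-person recall qualifies, the diet baseline is noisier. Under the prospective alternative, the first session is slightly delayed.
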